7.2 Efficacy Analyses

A listings of investigator determined best overall response (BOR) obtained on this study will be provided. BOR is defined as the best time point response that a subject achieves during the course of the study, with the response ranked according to the following order (from best to worst): complete response (CR)>complete response with incomplete marrow recovery (CRi)>partial response (PR)>partial response with lymphocytosis (PRwL)>stable disease (SD)>progressive disease (PD) (CRi applies to CLL only).

7.3 Safety Analyses

7.3.1 Adverse Events

Adverse events will be coded using MedDRA Version 19. The Grade of the AE will be assessed according to the NCI-CTCAE Version 4.03. If an AE is not included in the NCI-CTCAE Version 4.03, the Grade of the AE will be assessed according to the protocol, Section 8.2.1.2.

The summary of AEs will be focused on treatment-emergent AEs. Since this is an extension study, a treatment-emergent AE (TEAE) is defined as any AE that is reported out to 30 days after the last dose of study treatment. The onset date of an AE will be compared to the last dose date plus 30 days to determine whether the AE is treatment-emergent or not.

TEAEs will be summarized for each treatment arm by MedDRA system organ class (SOC) and preferred term (PT), or PT only. For summary tables by SOC and PT, SOC will be sorted alphabetically and PT will be sorted by decreasing frequency in the duvelisib arm within each SOC. For summary tables by PT only, PT will be sorted by decreasing frequency in the duvelisib arm.

If multiple TEAEs of the same PT occur within a subject, only the maximum grade observed for this PT will be used in summary of TEAEs by grade, the subject will be counted only once in the number of subjects for this PT and only once for the number of subjects for the SOC to which this PT belongs.

An overview TEAE summary table will be provided, which will include the number of subjects with AEs in selected categories. In addition, TEAEs will be summarized for the following categories, and will be tabulated by SOC and PT, unless otherwise specified.

- Treatment-emergent AEs
- Treatment-emergent AEs related to duvelisib
- Treatment-emergent AEs leading to treatment discontinuation
- Treatment-emergent AEs by maximum grade
- Grade 3 or higher treatment-emergent AEs
- Treatment-emergent SAE
- Treatment-emergent SAE related to duvelisib

Adverse events of special interest (AESI) will be summarized overall and with grading specifications. The AESI categories and associated PT's are provided in Appendix A of this document.

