**Exclusion Criteria:**

Any subject is to be excluded from the study if he or she:

1. Is unwilling or unable to comply with the requirements of the protocol

Subjects actively receiving duvelisib are to be excluded from this study if they:

1. Have any ongoing  $\geq$  Grade 3 AE considered related to duvelisib treatment at screening
2. Are pregnant or nursing

**Statistical Considerations:**Sample Size Determination

Not applicable.

Analysis Set

The All-Treated Analysis Set (ATS) will include all subjects who receive any amount of duvelisib on or after Cycle 1 Day 1 (C1D1) of this study. The ATS will be the primary analysis set for all safety endpoints.

Primary Analyses

Adverse events will be coded by using the Medical Dictionary for Regulatory Activities (MedDRA) version 16.1 or higher and will be graded according to the National Cancer Institute (NCI) Common Terminology Criteria for Adverse Events (CTCAE), version 4.03 or higher.

Summaries of AEs will be focused on treatment-emergent AEs (TEAEs). In this long-term extension study, a TEAE is defined as any AE with an onset date on or after C1D1 and within 30 days after the last dose of duvelisib. Treatment-emergent AEs will be summarized by MedDRA system organ class and preferred term. Separate summaries for TEAEs related to duvelisib, TEAEs that led to treatment discontinuation, TEAEs that led to death, TEAEs by CTCAE grade, TEAEs of Grade 3 or higher, serious TEAEs, and serious TEAEs related to duvelisib will be provided.

Baseline laboratory values will be those collected at C1D1 in this long-term extension study or, if not available, the most recent values collected within 30 days before C1D1. Applicable laboratory values will be graded according to CTCAE criteria. Shifts from baseline to maximum postbaseline grades will be tabulated for hematology, blood chemistry, and liver function tests.

Secondary Analyses:

Analyses of efficacy endpoints may be performed, as appropriate, according to the statistical analysis plan of the subject's previous study. No analyses of efficacy endpoints are planned for this study.

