## 8.2. Procedures for Eliciting, Recording, and Reporting Adverse Events

### 8.2.1. Eliciting and Recording Adverse Events

Subjects will be instructed to report all AEs and will be asked a general health status question at each study visit. All AEs occurring in eligible subjects will be recorded in the eCRF from the time the subject takes the first dose of duvelisib on this study (C1D1) through 30 days after the last dose of duvelisib. An AE will be followed until it is either resolved, has returned to baseline, or is determined to be a stable or chronic condition. All SAEs occurring from the signing of the ICF through 30 days after the last dose of duvelisib will be processed as outlined in [Section 8.2.2.](#)

At each required visit during the trial, all AEs that have occurred since the previous visit must be reviewed by the Investigator or designee. The Investigator or designee must determine if the AE is serious or nonserious.

The Investigator must assign the following AE attributes:

- AE diagnosis or syndrome(s) if known
  - If not known at time of the report, record the signs and/or symptoms as AEs and provide an updated report with diagnosis when obtained
- Dates of onset and resolution
- Severity as defined in this protocol
- Assessment of relatedness to duvelisib, and
- Action taken with duvelisib as a result of the AE

In general, an AE that is the primary cause of subsequent events should be identified by the primary cause (eg, for dehydration due to diarrhea, the AE would be diarrhea). However, AEs occurring secondary to an initiating event that are separated in time should be recorded as independent events (eg, sepsis secondary to pneumonia, both events should be recorded).

Progression of disease should not be reported as an AE/SAE but rather the signs and/or symptoms manifesting as the progression of disease should be reported (eg, for dyspnea due to progression of disease, the AE would be dyspnea). All fatal events must be reported as an SAE.

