### 9.4. Safety Analyses

Adverse events will be coded by using the Medical Dictionary for Regulatory Activities (MedDRA) version 16.1 or higher and will be graded according to the CTCAE, version 4.03 or higher.

Summaries of AEs will be focused on treatment-emergent AEs (TEAEs). In this long-term extension study, a TEAE is defined as any AE with an onset date on or after C1D1 and within 30 days after the last dose of duvelisib. TEAEs will be summarized by MedDRA system organ class and preferred term. Separate summaries for TEAEs related to duvelisib, TEAEs that led to treatment discontinuation, TEAEs that led to death, TEAEs by CTCAE grade, TEAEs of Grade 3 or higher, serious TEAEs, and serious TEAEs related to duvelisib will be provided.

Baseline laboratory values will be those collected at C1D1 of this long-term extension study, or if not available, the most recent values collected within 30 days before C1D1. Applicable laboratory values will be graded according to CTCAE criteria. Shifts from baseline to maximum postbaseline grades will be tabulated for hematology, blood chemistry, and LFTs.

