1 INTRODUCTION

This is the statistical analysis plan (SAP) for study IPI-145-23, *A Long-term, Continued Treatment and Follow-up Study in Subjects with Hematologic Malignancies Treated with Duvelisib (IPI-145)*. This SAP is prepared according to Amendment 1 of the protocol, dated 30 November 2017.

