8 CHANGES IN PLANNED ANALYSES

8.1 Changes in Planned Analyses from Protocol Amendment 1 to SAP V1.0

AESIs were not defined in Protocol Amendment 1. An analysis of AESIs is included in this SAP and the AESIs are defined in Appendix A.

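### SAP 7.3.1 omits the protocol's lower limit on TEAE onset (Cycle 1 Day 1), and SAP 8.1 does not declare the difference

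*SAP*

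**What the plan says.** Adverse events are one of the two primary endpoints (Protocol 3.1, SAP 5.1), and the summaries are built on treatment-emergent events.

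- **Protocol 9.4 and the synopsis** (under Primary Analyses) give the same rule, with two limits: "any AE with an onset date on or after C1D1 and within 30 days after the last dose of duvelisib".
- **SAP 7.3.1** sets one: "a treatment-emergent AE (TEAE) is defined as any AE that is reported out to 30 days after the last dose of study treatment". Its operational sentence follows suit: "The onset date of an AE will be compared to the last dose date plus 30 days". Nothing is compared with C1D1. The definition also speaks of when an event is reported, while the next sentence uses its onset.
- **SAP 6.2.1** classes an AE with a completely missing start date as treatment-emergent, without looking at the stop date.
- **SAP 8.1** gives one change from the amended protocol: "An analysis of AESIs is included in this SAP and the AESIs are defined in Appendix A". The TEAE definition is not mentioned.
- **SAP 1** identifies the protocol version it follows: "This SAP is prepared according to Amendment 1 of the protocol, dated 30 November 2017".

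**The concern.** The TEAE definition decides which events enter the main safety tables. A programmer working from the SAP would apply one date test where the protocol requires two. An event with onset before C1D1 would then be a TEAE under the SAP and not under the protocol.

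The protocol foresees such events. Non-serious AEs are recorded only from first dose, but serious events are collected from consent: "All SAEs occurring from the signing of the ICF through 30 days after the last dose of duvelisib". A serious event between consent and first dose would be counted in this study's treatment period although it began before that period.

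The direction is known: the SAP rule can only add events, so it cannot hide harm. Treated subjects also arrive already receiving duvelisib (Protocol 5.1, within 14 days of study entry). The error would therefore be one of placing the event in the wrong study period, not of tying it to a drug the subject had never taken.

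**Working it through.** The documents give no figure to reproduce. The check compares the two rules and then asks which events can fall between them.

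**1. The two tests**

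| Onset date | Protocol: C1D1 ≤ onset ≤ last dose + 30 days | SAP: onset ≤ last dose + 30 days |
|---|---|---|
| Before C1D1 | not a TEAE | TEAE |
| C1D1 to last dose + 30 days | TEAE | TEAE |
| After last dose + 30 days | not a TEAE | not a TEAE |

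They differ only in the first row.

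**2. Does another SAP section supply the lower limit?** No.

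- 4.1 refers to C1D1 to select subjects, not events.
- 6.2.1 points back to 7.3.1.
- 6.8 concerns baseline laboratory values.
- 7.1.3 uses the first dose date only for duration of exposure.

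**3. Which pre-C1D1 events could be in the AE data?**

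- Non-serious AEs: largely excluded at collection. Protocol 8.2.1 says "All AEs occurring in eligible subjects will be recorded in the eCRF from the time the subject takes the first dose of duvelisib", Table 1 footnote l agrees, and 6.2.7 sends conditions arising between consent and first dose to medical history.
- Preexisting conditions that have not worsened: not AEs under Protocol 8.1.1.
- Serious AEs between consent and C1D1: collected under Protocol 6.2.7, 8.2.1 and 8.2.2 through the SAE Report Form. No section expressly sends them to the AE page of the eCRF. Protocol 10.5 provides eCRFs for recording all data, so entry is not excluded.

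**4. How long is the gap?** Table 1 has no separate screening column and places consent in the C1D1 column. If consent and first dose fall on the same day, the gap is 0 days and this source adds nothing. Protocol 6.1 does, however, refer to a screening period, and 6.2.7 regulates events between consent and first dose, so a gap is possible.

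**5. Effect of one event.** SAP 7.3.1 lists 7 TEAE categories: all, related, leading to discontinuation, by maximum grade, Grade 3 or higher, serious, and serious related. A pre-C1D1 serious event falls in at least 3 of them (all, by maximum grade, serious). Whether it enters the other 4 depends on the event.

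If the subject has no other TEAE, the any-TEAE and serious-TEAE percentages each rise by 100/N points, where N is the number of treated subjects. The documents give no N, so the values below are assumptions:

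| Assumed N | 100/N |
|---|---|
| 25 | 4.0 points |
| 50 | 2.0 points |
| 100 | 1.0 point |

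SAP 6.1 reports percentages to one decimal, so any of these shifts would be visible.

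**The case against.** The strongest reply is that data collection already supplies the missing limit. AEs are recorded from first dose, pre-dose conditions go to medical history with no stated exception for serious ones, and early SAEs travel on a separate form. On AE data collected that way, both definitions select the same events. The remaining case needs consent before the dosing day, a serious event in the gap, a subject who is still dosed, and entry on the AE page. This stands as a limit on size. It does not make the stated rule correct: the protocol sets the limit expressly, and the analysis should not depend on data-entry practice to apply it.

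Four further points:

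- **The SAP gives a reason.** Its sentence opens by citing the extension design. But Protocol 9.4 sets the C1D1 limit for this same extension study, so that reason does not explain dropping it.
- **The SAP may modify methods.** Protocol 9 allows this and asks for an amendment only when the change is major. No breach of that rule is claimed; the difference simply belongs in 8.1.
- **100/N holds for any single subject in any table.** True. It shows what one event would do, not how many there are.
- **The missing-date rule in 6.2.1 contradicts nothing in the protocol and is cautious.** True as far as it goes. Yet an event known to have ended before C1D1 cannot have started on or after it, so the stop-date check follows from the protocol's definition.

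**Conclusion.** The concern holds and is minor. The SAP's TEAE rule differs from the protocol's, nothing else in the SAP corrects it, and 8.1 does not declare it.

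The realised effect may be zero and cannot be estimated from the documents. If an affected event occurs, it can only inflate counts, by 100/N percentage points for each newly counted subject. SAP 3.5 plans no formal inference, so only descriptive summaries are affected.

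Two assumptions matter. First, the statement about 8.1 assumes that the supplied protocol is Amendment 1; its title page was removed, so this cannot be confirmed. Second, any effect from early serious events assumes that they are entered in the AE dataset, which the documents neither require nor rule out.

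**What to change.** - **SAP 7.3.1:** define a TEAE by onset on or after C1D1 of this study and no later than 30 days after the last dose, and compare onset with both dates. Use onset throughout, not the time of reporting.
- **Pre-C1D1 serious events:** list separately any SAE with onset between consent and C1D1, so that none is lost from view.
- **SAP 6.2.1:** do not class an AE with a completely missing start date as treatment-emergent when its stop date is before C1D1.
- **Alternative:** if the lower limit was dropped on purpose, state and justify this in SAP 8.1.

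The cost is one clause, one sentence, one extra date comparison and a short listing. No new data item is needed, because SAP 7.1.3 already uses the date of first dose in this study. The only downside is a possibly slightly lower TEAE count.

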7.3.2 Laboratory Data

Laboratory tests will be reported separately for hematology and blood chemistry.

For the purposes of presentation in listings, the following laboratory test results will be converted to the International System of Units (SI) before presentation: sodium, potassium, chloride, bicarbonate (or CO₂), albumin, total protein, creatinine, uric acid, calcium, phosphorus,

magnesium, glucose, total and direct bilirubin, and alkaline phosphatase, red blood cell (RBC) count, hemoglobin, hematocrit, platelets, white blood cell count with 5-part differential performed manually or by flow cytometry (lymphocytes, neutrophils, monocytes, basophils, and eosinophils), etc.

7.3.3 Overall Survival

A listing of each subject's last survival status will be provided, including total time on study. If the subject has died, cause of death will be provided.

8 CHANGES IN PLANNED ANALYSES

8.1 Changes in Planned Analyses from Protocol Amendment 1 to SAP V1.0

AESIs were not defined in Protocol Amendment 1. An analysis of AESIs is included in this SAP and the AESIs are defined in Appendix A.

10 APPENDICES

10.1 Appendix A

Adverse Events of Special Interest (AESI)

AESI	MedDRA Version 16.1 Grouped Preferred Terms
Diarrhoea/Colitis & Diarrhoea GE Grade 3/Colitis GE Grade 2	Colitis Colitis erosive Colitis microscopic Colitis ulcerative Enterocolitis Enterocolitis haemorrhagic Necrotising colitis Diarrhoea Diarrhoea haemorrhagic
Infection (including pneumonia) & Infection (including pneumonia) GE Grade 3	Each PT in the Infections and Infestations SOC

AESI	MedDRA Version 16.1 Grouped Preferred Terms
Neutropenia & Neutropenia GE Grade 4	Neutropenia Neutrophil count decreased
Pneumonitis & Pneumonitis GE Grade 2	Acute interstitial pneumonitis Interstitial lung disease Lung infiltration Pneumonitis
Severe Cutaneous Reactions (Rash) & Severe Cutaneous Reactions (Rash) GE Grade 3	Dermatitis Dermatitis bullous Dermatitis exfoliative Dermatitis exfoliative general Drug eruption Drug reaction with eosinophilia and systemic symptoms Erythema Erythema multiforme Exfoliative rash Generalised erythema Mucocutaneous rash Palmar erythema Perivascular dermatitis Plantar erythema Rash Rash erythematous Rash follicular Rash generalised Rash macular Rash maculo-papular Rash maculovesicular Rash papular Rash mapulosquamous Rash pruritic Rash pustular Rash vesicular

AESI	MedDRA Version 16.1 Grouped Preferred Terms
	Skin reaction Skin toxicity Stevens-Johnson syndrome Toxic epidermal necrolysis Toxic skin eruption
Transaminase elevation & Transaminase elevation GE Grade 3	Acute hepatic failure Alanine aminotransferase increased Aspartate aminotransferase increased Drug-induced liver injury Hepatic enzyme increased Hepatic failure Hepatocellular injury Hepatotoxicity Transaminases increased

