3.5 Planned Analyses

There are no formal inferential statistical analyses planned for this study.

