6.9 Computing and Coding Standards

Activities will be performed using the following tools:

Table, listing, and figure production	SAS Version 9.4 or higher
Coding	
Adverse Events	MedDRA Version 19
Medical Histories	MedDRA Version 19
Prior and Concomitant Medications	WHODrug WHO-DD Sep-15
Grading	
AEs	CTCAE Version 4.03 or higher

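### SAP Appendix A gives its AESI term lists under MedDRA 16.1 while adverse events are coded in MedDRA 19, and one rash entry is misspelt

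*SAP*

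**What the plan says.** SAP 7.3.1 fixes the coding dictionary: "Adverse events will be coded using MedDRA Version 19". The coding table in SAP 6.9 names the same version for adverse events, "MedDRA Version 19". Protocol 9.4 sets version 16.1 as a minimum.

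The AESI analysis is also in SAP 7.3.1: "Adverse events of special interest (AESI) will be summarized overall and with grading specifications". For the categories and their terms it says only that they "are provided in Appendix A of this document". SAP 8.1 explains that Protocol Amendment 1 defined no AESIs, and adds: "An analysis of AESIs is included in this SAP and the AESIs are defined in Appendix A".

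The term column of the Appendix A table is headed "MedDRA Version 16.1 Grouped Preferred Terms", and the heading is repeated on each part of the table. There are six categories. Five are typed lists of preferred terms. The sixth, infection, takes every preferred term in one SOC. The rash list includes *Rash mapulosquamous*.

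**The concern.** A grouped AESI summary counts a subject when a coded preferred term is on the category's list. The list and the coded data therefore need to use the same vocabulary. Here the lists carry one dictionary version and the data another, and no section says the two were compared. Because the protocol defines no AESIs, a programmer has no second source against which to settle a doubtful term.

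The misspelling is the more concrete problem. Appendix A prints term names without dictionary codes, and the SAP does not say how terms are to be matched. Applied as printed, the entry selects nothing. An event coded to the intended term would then be left out of the rash AESI, both overall and at Grade 3 or higher, and nothing in the output would show the omission. Safety is the primary objective and adverse events are a primary endpoint, so the lists should be right before the tables are built.

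**Working it through.** The plan gives no figure to reproduce. The check is a comparison of sections and a count of entries.

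**1. Versions.**

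| Place | MedDRA version | Role |
|---|---|---|
| Protocol 9.4 | 16.1 or later | Minimum for coding |
| SAP 6.9 | 19 | Coding |
| SAP 7.3.1 | 19 | Coding |
| SAP Appendix A | 16.1 | AESI term lists |

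Version 19 satisfies the protocol minimum, so the coding version is not in doubt. The mismatch is inside the SAP, between the coding and the lists.

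**2. Stated reconciliation.** SAP 7.3.1 points to Appendix A, and SAP 8.1 records that the AESI analysis was added. Neither mentions a mapping or a review against version 19, and no other section does.

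**3. Scope.** Entries in Appendix A by category:

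- Diarrhoea/colitis: 9
- Neutropenia: 2
- Pneumonitis: 4
- Rash: 31
- Transaminase elevation: 9
- Infection: no typed list (SOC rule)

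Total: 9 + 2 + 4 + 31 + 9 = 55 entries in five lists, with no duplicates.

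**4. The misspelt entry.** Twelve of the 31 rash entries begin with the word *Rash*, and they run alphabetically apart from one. *Rash mapulosquamous* stands between *Rash papular* and *Rash pruritic*. A word starting with *m* does not belong there, whereas *papulosquamous* does. No other entry contains *squam*, so the evidently intended term is not listed under a correct spelling. The misspelling is 1 entry of 55 and touches one category of six. That share says nothing about the share of events.

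**5. Consequence under each way of matching.**

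- Text matching: the entry matches no coded term. An event coded to the intended term is missed in the overall rash summary and, if it is Grade 3 or higher, in that summary as well.
- Matching by dictionary code after a look-up: the entry has no code to find, so the error either comes to light or the entry is dropped.
- A listed term that differs in version 19: events under that term might be missed, while the unchanged terms in the same list still match.

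**6. What is unaffected.** The main treatment-emergent adverse event tables do not use Appendix A; they "will be tabulated by SOC and PT, unless otherwise specified". They include a Grade 3 or higher table. An event missed by a grouping is still counted there under its own preferred term.

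**The case against.** The strongest reply is that no wrong count has been shown. The documents contain neither dictionary version, so they cannot show that any listed term was renamed, moved or added between 16.1 and 19. The heading may only record where the lists came from, and a SAP that describes no check has not shown that none was made. This stands. A reader might infer that the AESI counts are wrong or that a whole category would fail, and the documents support neither inference.

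A reader might also infer that the infection category is out of date because it sits under the same heading. It is a rule, not a list: it takes whatever is coded to that SOC, and coding is in version 19. It needs no separate change. Nor is there a protocol breach, since version 19 is above the stated minimum.

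On the misspelling, the loss depends on how terms are matched, on the intended term being a preferred term in the coding version, and on an event being coded to it. None of these is known. The text was also machine-read from PDF, so a reading error is not excluded, although a clean change of first letter makes one unlikely.

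Finally, the stakes are limited. The AESI analysis is a descriptive addition, and SAP 3.5 says: "There are no formal inferential statistical analyses planned for this study". Protocol 8.2.2.1 separately requires Grade 3 or higher rash to be reported within 24 hours. That is a reporting route and does not correct a table, but severe rash would not go unnoticed for want of an Appendix A entry.

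What survives is that Appendix A is an operative list. One entry cannot work as printed, and the other 54 have no stated check against the version in use.

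**Conclusion.** The point holds, at low severity. Two things are established with high confidence from the text: the version mismatch between the coding and the five fixed lists (55 entries), and an evident misspelling in the rash list with no correctly spelt counterpart.

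The effect on AESI counts cannot be sized from the documents and may be zero. It rests on three unknowns: the matching method, the content of the two dictionary versions, and whether any event is coded to an affected term. If there is an effect, it is confined to the AESI summaries.

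**What to change.** Before the AESI tables are programmed:

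- check the five fixed lists against the MedDRA version used for coding;
- correct *Rash mapulosquamous* to the intended preferred term, confirmed in that version;
- re-issue Appendix A with its heading showing that version.

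The cost is one dictionary check of 55 entries and a revised appendix. Data collection, the coding and the SOC/PT tables do not change.

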**Table 4: Dose Holds for Treatment-related Adverse Events**

| Treatment-related Toxicity a,b                              | Duvelisib c   |
|--|--|
| Hematologic   |  |
| ≥ Grade 3 FN   | Hold until afebrile and negative culture                                 |
| ≥ Grade 3 Thrombocytopenia with ≥ Grade 2 Hemorrhage                   | Hold until no evidence of hemorrhage and stabilization of platelet count |
| Other Grade 4 Hematologic Toxicity (excluding FN and Thrombocytopenia) | Continue   |
| Nonhematologic  |  |
| ≥ Grade 2 Pneumonitis/Pneumonia  | Hold until completion of course of therapy and resolution of symptoms    |
| ≥ Grade 3 Nonhematologic Toxicity                                      | Hold until ≤ Grade 1 or return to Baseline                               |

Abbreviations: AE = adverse event; CTCAE = Common Terminology Criteria for Adverse Events; FN = febrile neutropenia.

a Treatment-related AEs: possible, probable, or definite relationship to duvelisib.

b Toxicity grades are defined per CTCAE Version 4.03. Note if a parameter is not defined by CTCAE, then AE grading criteria ([Section 8.2.1.2](#)) should be utilized.

c Dosages of duvelisib may be reduced after subsequent occurrences of the same treatment-related AE. See [Section 7.2.1](#) for more information on dosing modification and discontinuation.

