#### 8.2.1.3. Abnormal Laboratory Values

The Investigator is responsible for reviewing laboratory test results and determining whether an abnormal value in a subject represents a clinically significant change from the subject's baseline value. In general, abnormal laboratory findings without clinical significance (based on the Investigator's judgment) should not be recorded as AEs. In general, abnormal laboratory test results should be reported as an AE if the laboratory result:

- requires an adjustment or discontinuation of duvelisib
- requires treatment or adjustment to current therapy
- is considered to be an AE by the Investigator

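### The neutropenia event of special interest omits febrile neutropenia, so its grouped subject count is too low by the subjects who have only that term

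*SAP*

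**What the plan says.** SAP Section 7.3.1 summarizes each AESI category overall and at a stated grade cut, and refers to Appendix A for the preferred terms. SAP Section 8.1 names the AESI analysis as the change from the protocol's planned analyses.

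In Appendix A the neutropenia category is headed "Neutropenia & Neutropenia GE Grade 4" and its complete term list is "Neutropenia Neutrophil count decreased". The infection category is headed "Infection (including pneumonia) & Infection (including pneumonia) GE Grade 3" and takes in "Each PT in the Infections and Infestations SOC".

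Protocol Table 4 places febrile neutropenia at Grade 3 or above in its hematologic block as a reason to hold duvelisib, and Protocol Section 7.2.1.1 repeats this. For other Grade 4 hematologic toxicity, the same table and section allow dosing to go on.

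**The concern.** A grouped AESI row exists to give one number: how many subjects had the condition under any of its names. The neutropenia row leaves out the name that carries the febrile form. Its graded row starts at Grade 4, so it counts non-febrile events that need not interrupt dosing, while febrile neutropenia is counted at no grade.

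Long-term safety is the primary objective and adverse events are a primary endpoint, so a reader will probably take the AESI row as the study's neutropenia rate. That rate would omit subjects whose only recorded neutropenic event was febrile.

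**Working it through.** The documents state no figure for this point, so the check is a comparison of lists, followed by the arithmetic of the grouped count.

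**Step 1: term lists.** The listed terms in Appendix A number 9 for diarrhoea/colitis, 2 for neutropenia, 4 for pneumonitis, 31 for rash and 9 for transaminase elevation: 9 + 2 + 4 + 31 + 9 = 55. None of the 55 is febrile neutropenia. The infection category is defined by a whole system organ class (SOC). The documents do not say to which class febrile neutropenia is coded. Protocol Table 4 files it as hematologic, which fits a place outside infections. In either case it is not in the neutropenia row.

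**Step 2: protocol hold triggers beside AESI rows.**

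| Event | Hold trigger in the protocol | AESI overall row | AESI graded row |
|---|---|---|---|
| Febrile neutropenia | Grade ≥3 | none by name | none by name |
| Grade 4 neutropenia without fever | none by grade | neutropenia | Grade ≥4 |
| Pneumonia | Grade ≥2 | infection | Grade ≥3 |
| Pneumonitis | Grade ≥2 | pneumonitis | Grade ≥2 |
| Diarrhoea | Grade ≥3 | diarrhoea/colitis | Grade ≥3 |
| Rash | Grade ≥3 | rash | Grade ≥3 |
| ALT/AST elevation | Grade ≥3 | transaminase | Grade ≥3 |
| Thrombocytopenia with hemorrhage; nausea/vomiting; cardiac/QTcF | yes | none | none |

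**Step 3: the SAP's own grouping practice.** The rash list includes Stevens-Johnson syndrome and toxic epidermal necrolysis. The transaminase list includes hepatic failure and drug-induced liver injury. Those categories carry their severe clinical forms; the neutropenia category does not.

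**Step 4: can a subject have febrile neutropenia and no listed term?** Yes. Protocol Section 8.2.1 asks for the diagnosis or syndrome where it is known. Protocol Section 8.2.1.3 says that, in general, "abnormal laboratory findings without clinical significance" are not recorded as adverse events, so a low count before the fever may leave no separate neutropenia record.

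**Step 5: size.** Let A be the subjects with at least one listed term and F the subjects with febrile neutropenia and no listed term. The row shows A; with the term added it would show A + F. The absolute shortfall is F and the relative shortfall is F/(A + F). The documents give neither A nor F. Assumed counts, for illustration only, in 100 treated subjects:

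- A = 20, F = 2: 20% shown against 22%; shortfall 2/22 = 9.1%.
- A = 20, F = 5: 20% shown against 25%; shortfall 5/25 = 20%.

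**Step 6: can the other tables supply the number?** SAP Section 7.3.1 counts a subject once within each preferred term, so term rows cannot be added when subjects overlap. If T subjects have febrile neutropenia in all, the combined count lies between max(A, T) and A + T. With A = 20 and T = 5 that is 20 to 25. The tables bound the answer but do not give it.

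**The case against.** **The events are reported elsewhere.** This stands. SAP Section 7.3.1 tabulates all treatment-emergent events by SOC and preferred term and by maximum grade, with a separate table for Grade 3 or higher. Febrile neutropenia appears there, and SAP Section 7.1.3 counts subjects with a dose hold. What is missing is the grouped subject count (Step 6).

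**A subject with febrile neutropenia may be counted anyway.** Also correct. Protocol Section 8.2.1 has secondary events that are separated in time recorded independently, so an earlier neutropenia record would bring the subject into the row. The gap concerns only subjects without such a record.

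**Nothing ties the AESI list to the hold table.** This stands as well. The SAP does not say that the two must agree, and Step 2 shows departures in both directions. Holds apply to treatment-related events, whereas the AESI rows carry no such limit. The case therefore rests on the category's own purpose and on how the rash and transaminase lists are built. The hold rule shows only that the protocol regards febrile neutropenia as important.

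**Stronger readings that a reader might infer:**

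- *Pneumonia is undercounted.* The protocol holds for "≥ Grade 2 Pneumonitis/Pneumonia", while the category "Pneumonitis & Pneumonitis GE Grade 2" lists only "Acute interstitial pneumonitis Interstitial lung disease Lung infiltration Pneumonitis". Grade 2 pneumonia is therefore in no graded AESI row. It is, however, counted in the overall infection row and in the maximum-grade table. Its absence from a Grade 3 row is simply what that cut means.
- *Laboratory Grade 4 neutropenia is missed.* Protocol Section 6.2.4 includes the absolute neutrophil count, and Protocol Section 9.4 requires CTCAE grading with shifts from baseline to the maximum grade for hematology. Those tables cover it. Whether SAP Section 7.3.2 carries them forward is a separate question and not a fault of Appendix A.
- *The plan makes duvelisib look safer.* The study is open-label and without formal inference, and no event leaves the safety report. The documents support a low count in one grouped category and nothing wider.

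**Conclusion.** The point holds for febrile neutropenia alone. The neutropenia AESI overall row is too low by F, the number of subjects with treatment-emergent febrile neutropenia and no separately recorded listed term. F may be zero and cannot be computed from the documents; the 9.1% to 20% range depends entirely on assumed counts. The conclusion assumes that events are coded to febrile neutropenia as a term of its own and that Appendix A is applied as written. It is a small correction to a grouped primary-safety summary. It is not a gap in data capture and not evidence of bias in the safety report as a whole.

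**What to change.** In SAP Appendix A:

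1. Add febrile neutropenia to the neutropenia category. Keep the existing overall and Grade 4 rows, now based on three terms.
2. Show febrile neutropenia also as its own row, at any grade and at Grade 3 or higher. Without this row, a Grade 3 event would enter the overall neutropenia row but no graded one.
3. Add a footnote saying that subjects can appear in both sets of rows and that the rows must not be summed.

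If the omission is deliberate, one sentence giving the reason would serve instead. The cost is one term, one or two table rows and a footnote; no data collection and no clinical rule changes.

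Optional: a combined pneumonitis/pneumonia row at Grade 2 or higher would show that protocol event as a single count. It would need its pneumonia terms listed explicitly and the same overlap footnote. No laboratory row is needed here.
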